3.5.8 NAPI Set

The NAPI Set (NAPIS) will consist of subjects in the FAS with nail disease at Baseline.

3.5.9 Blinded Maintenance Set

The Blinded Maintenance (BM) Set is defined as follows: Analyses based on either SS, FAS, PPS, PsAS, NAPI will be based on BM SS, BM FAS, BM PPS, BM PsAS or BM NAPI for the Interim Analysis, where the BM Set will consist of all subjects in the respective analysis set who do not discontinue treatment during Initial Period and who are PASI 50 responder at week 16 (do not escape planned treatment). All analysis sets with prefix BM are based on these additional conditions.

For final analysis, analyses based on BM sets will include all data observed during blinded treatment only (including data at escape visit, if applicable). Escapers at Week 16 will be included in tables by blinded maintenance treatment with their observed value at Week 16 and imputed data after escape. This is different as done for Interim Analysis which did not take escapers into account.

3.5.10 Escape Maintenance Set

The Escape Maintenance (EM) Set is only applicable for the final analysis. Analysis sets EM SS, EM FAS, EM PsAS and EM NAPSI are introduced for the final analysis, where the EM Set will consist of all subjects in the respective analysis set (SS, FAS, PsAs and NAPSI) who do not discontinue treatment during Initial Period and who have received at least 1 dose of escape study medication during the Maintenance Period. Analyses based on EM sets will include only data observed during escape treatment.

3.5.11 Cohort Enrolled Set

The Cohort Enrolled Set (CES) will consist of subjects with erythrodermic PSO or generalized pustular PSO who have given informed consent.

3.5.12 Cohort Randomized Set

The Cohort Randomized Set (CRS) will consist of subjects with erythrodermic PSO or generalized pustular PSO randomized into the cohort.

3.5.13 Cohort Safety Set

The Cohort Safety Set (CSS) will consist of subjects with erythrodermic PSO or generalized pustular PSO in the CRS who have received at least 1 dose of study medication.

3.5.14 Cohort Full Analysis Set

The Cohort Full Analysis Set (CFAS) will consist of subjects in the CRS who received at least 1 dose of the study medication, subjects with generalized pustular PSO have valid efficacy assessment (JDA score) for baseline and for at least 1 post baseline visit, or subjects with erythrodermic PSO have valid efficacy assessments (PASI score) for baseline and for at least 1 post baseline visit.

3.5.15 Cohort Pharmacokinetics Set

The Cohort Pharmacokinetics Set (CPKS) will consist of subjects with erythrodermic PSO or generalized pustular PSO randomized into the cohort who took at least 1 dose of the study medication and provided at least 1 quantifiable CZP plasma concentration.

3.5.16 Erythrodermic PSO Set

The Erythrodermic PSO Set (EPS) will consist of subjects in the CFAS with erythrodermic PSO disease at Baseline.

3.5.17 Generalized Pustular PSO Set

The Generalized Pustular PSO Set (GPPS) will consist of subjects in the CFAS with generalized pustular PSO disease at Baseline.

3.6 Treatment assignment and treatment groups

All safety analyses and pharmacokinetic analyses will be based on actual treatment assignment, whereas all efficacy analyses will be based on randomized treatment assignment, unless specified otherwise. Analyses for escapers will be based on Escape Maintenance Treatment Group or on the latest dose of study medication the subject received before escape.

3.6.1 Subjects with plaque PSO

Period 2 – Initial Period - Week 0 to Week 16

Efficacy and Safety Evaluations:

During the 16-week Period 2, efficacy and safety data will be presented by the following treatment groups:

- PBO
- CZP 200mg Q2W
- CZP 400mg Q2W

Selected variables (where stated in the following sections) may be summarized by treatment group and subgroup (Definition of subgroups, see [Section 4.8](#)).

Period 3 – Maintenance Period - Week 16 to Week 52

Efficacy Evaluations – Blinded Maintenance Period:

During the 36-week Period 3, subjects will be allocated to dose groups based on their Week 16 PASI50 response. For efficacy, data will be summarized separately for those subjects remaining in the blinded part of the study (including data at escape visit if applicable) and those subjects who switched to the Escape Arm. For those in the blinded part of the study, efficacy data will be summarized based upon the treatment group assigned at Week 0 and the treatment group assigned at Week 16, using the following blinded maintenance treatment groups:

- PBO/PBO
- CZP 200mg Q2W/CZP 200mg Q2W + CZP 200mg Q2W/CZP 400mg Q4W
- CZP 400mg Q2W/CZP 400mg Q2W
- CZP 200mg Q2W/CZP 200mg Q2W
- CZP 200mg Q2W/CZP 400mg Q4W

Subjects who escape during the Maintenance Period will be displayed until their escape visit using the treatment groups listed above. Placebo escapers at Week 16 will be presented in PBO/PBO, escapers at Week 16 from CZP 200mg Q2W in CZP 200mg Q2W/CZP 200mg Q2W and escapers at Week 16 from CZP 400mg Q2W in CZP 400mg Q2W/CZP 400mg Q2W.

For efficacy, when data will be modelled (logistic regression), the combined treatment group ‘CZP 200mg Q2W/CZP 200mg Q2W + CZP 200mg Q2W/CZP 400mg Q4W’ will be dropped, because otherwise, subjects would be included twice and this would result in non-independent records and in violation of modelling assumptions.

For the interim analysis, the blinded maintenance treatment groups will be used within the Blinded Maintenance Set (Maintenance Period does not include any information for escapers in interim analysis).

For the final analysis, efficacy data collected during the Maintenance Period while on blinded treatment (including the visit on which the first escape study medication is administered) will be summarized by blinded maintenance treatment group in stand-alone tables based on Blinded Maintenance analysis set.

Efficacy Evaluations – Escape Arms:

Efficacy data collected during the Maintenance Period after the point of escape will be summarized in stand-alone tables using treatment groups consisting of the (re-)randomized treatment before escape and the escape information:

- PBO/Esc CZP
- CZP 200mg Q2W/Esc CZP
- CZP 400mg Q2W/Esc CZP
- CZP 400mg Q4W/Esc CZP

or/and using the following Escape Maintenance Treatment Groups:

- Esc CZP 200mg Q2W
- Esc CZP 400mg Q2W
- All Esc CZP (only for safety data)

Safety Evaluations - Blinded Maintenance Period:

Safety data of the Maintenance Period will be summarized by the following blinded treatment groups (include data only until escape if subject escapes; escape visit date inclusive unless it is an injection site reaction).

- PBO
- CZP 200mg Q2W
- CZP 400mg Q4W
- CZP 200mg Q2W + CZP 400mg Q4W
- CZP 400mg Q2W
- All CZP

Safety Evaluations - Escape Arms:

For those subjects who moved to the Escape Arm during Maintenance Period, safety data after the escape visit will be presented by the following escape maintenance treatment groups:

- Esc CZP 200mg Q2W
- Esc CZP 400mg Q2W
- All Esc CZP (only for safety data)

Combined Initial and Maintenance Period – Week 0 to Week 52

Selected efficacy data for the combined Initial and Maintenance Period will be summarized by randomized treatment group and maintenance treatment group.

Selected safety data for the combined Initial and Maintenance Period will be summarized using two different approaches. In the first approach, data will be summarized by the following blinded treatment groups (including data only until escape if subject escapes; escape visit date inclusive unless it is an injection site reaction):

- PBO
- CZP 200mg Q2W
- CZP 400mg Q4W
- CZP 200mg Q2W + CZP 400mg Q4W
- CZP 400mg Q2W

- All CZP

In the second approach, data will be summarized by the following treatment groups and regardless of whether the dose was administered as blinded or open-label treatment.

- PBO
- CZP 200mg Q2W
- CZP 400mg Q4W
- CZP 200mg Q2W + CZP 400mg Q4W
- CZP 400mg Q2W
- All CZP

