2.3.1 Study design for subjects with moderate to severe chronic plaque PSO

2.3.1.1 Period 1: Screening

The Screening Period of 2 to 5 weeks will be used to confirm eligibility; obtain laboratory data; verify that the doses of nonsteroidal anti-inflammatory drugs (NSAIDs) and other pain relievers, such as acetaminophen, paracetamol, or mild opiates, if used to treat PsA are stable; and enable washout of any medications not permitted for use during the study.

2.3.1.2 Period 2: Initial Period - Week 0 to Week 16

Eligible subjects will be allocated to the following study treatments in a 2:2:1 ratio:

- CZP 400mg Q2W (n=50): CZP administered sc at the dose of CZP 400mg Q2W

- CZP 200mg Q2W (n=50): CZP administered sc at the dose of CZP 400mg at Weeks 0, 2, and 4, followed by CZP 200mg Q2W (starting at Week 6)
- PBO (n=25): PBO administered sc Q2W

Study treatments (including PBO) will be administered by dedicated, unblinded, trained site personnel at Baseline and Q2W thereafter to Week 14. Week 16 is the last study visit during this period.

2.3.1.3 Period 3: Maintenance Period - Week 16 to Week 52

The treatment received in Period 3 will be based on response to double-blind treatment at Week 16. All CZP and PBO treatments will be administered by dedicated, unblinded, trained site personnel at site visits, excluding the escape treatment.

Subjects who achieve a PASI50 response at Week 16 will continue therapy as follows:

- Subjects initially randomized to CZP 400mg Q2W will continue to receive CZP 400mg Q2W.
- Subjects initially randomized to CZP 200mg Q2W will be re-randomized (1:1) to receive either CZP 200mg Q2W or CZP 400mg Q4W (with PBO administered on alternate dosing weeks to maintain the blind).
- Subjects initially randomized to PBO will continue to receive PBO.

Subjects who do not achieve a PASI50 response at Week 16, 24, 32, or 40 will escape from double-blind treatment and receive treatment as follows:

- Escape treatment: Subjects entering the escape arm of the study will receive open-label CZP treatment (400mg Q2W as 3 loading doses followed by CZP 200mg Q2W). Subjects receiving open-label CZP 200mg Q2W in the escape arm and not achieving a PASI50 response will be allowed to have their dose increased to CZP 400mg Q2W, at the discretion of the Investigator. If, in the opinion of the Investigator, the subject is not receiving benefit (eg, a PASI50) at the CZP 400mg Q2W dose, the subject should be withdrawn from the study.

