PASI50, PASI75, PASI90 and PASI100 responder rates (based on simple counts and percentages only) will be also summarized for the Blinded Maintenance Period (Week 16 through Week 24) by blinded maintenance treatment group (combined group inclusive) using NRI imputed and observed data.

A table summarizing the (exact) logistic regression analysis results of PASI75/PASI90 response rates during Blinded Maintenance Period based on the subset of PASI75/PASI90 responders at Week 16 will also be provided (observed case, NRI and MCMC imputed data), procedure as outlined in [Section 8.1.2](#). Additionally, the same table will be produced to summarize simple counts and percentages using the blinded maintenance treatment groups (combined group inclusive) based on NRI and observed data only.

Line plots will be generated to present the percentages of responders over time by blinded maintenance treatment group (Blinded Maintenance Period treatment) over time (from Week 16 to Week 24) based on MCMC imputed data.

Maintenance Period (Final Analysis, including subjects who escaped after Week 16)

The analysis of the PASI50, PASI75, PASI90, and PASI100 responder rate during the Maintenance Period will be based on the BM FAS. Missing data will be handled based on a combination of NRI and multiple imputation. The procedure is described below:

1. Identify subjects who met the escape criterion at any timepoint (ie, did not achieve a PASI50 response), and do not include them in the multiple imputation model described in Step 2.
2. For all subjects not identified in Step 1, create a data set, one for each treatment group, of subjects with observed values and those needing estimation by multiple imputation. The missing PASI values in each data set will be filled in using the MCMC method with a total of 75 sets of imputations being performed. The procedure will sequentially estimate an imputation model for the PASI score at each post-Baseline visit where PASI is collected, with prior biologic exposure and Baseline score as predictors. The resulting data sets for each treatment arm will be combined into one complete data set based on each of the 75 imputations.

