3. For the subjects meeting the escape criterion identified in Step 1, all visits after the point of escape will be imputed via NRI. This imputation is based on meeting the escape criterion, whether or not the subject actually received escape treatment. Once imputation has been performed for these subjects, these records are duplicated 75 times and combined with the 75 imputations performed in Step 2.

Note: If subjects identified here have intermittent missing data at earlier time points, those will be imputed via NRI.

4. For each complete imputed data set, the dichotomous PASI responder rate based on the PASI scores will be computed. Each complete imputed data set will then be analyzed using simple proportions by treatment group ($p=x/N$, where x is the number of responder and N the number of subjects in this treatment group). The corresponding standard error for the sample proportion will be calculated with the square root of $p(1-p)/N$.

Note: For derivation of PASI75 response, the imputed PASI value will be compared directly to the observed Baseline PASI value to determine whether or not a reduction of at least 50% (or 75%, 90%, 100%) was achieved. If values outside of the pre-defined range

of values for PASI (0-72) are imputed, they will be cut off as appropriate after the multiple imputation procedure but before deriving the responder variables. For example, an imputed PASI value of -0.5 would be changed to 0 before deriving the PASI responder variable.

5. The results at each week of each of the 75 imputed data sets will be combined into a single inference using SAS PROC MIANALYZE.

The estimated responder rates at each week will be presented by treatment group based on the FAS.

Additionally, NRI will be used for imputation of missing data. Simple proportions will be calculated to estimate responder rates at each visit in the Maintenance Period (ie, Week 16 through Week 52). Responder rates based on observed case data will also be summarized.

A table summarizing the PASI75/PASI90 response rates (simple proportions) during Maintenance Period based on the subset of PASI75/PASI90 responders at Week 16 will also be provided (observed case, NRI and MCMC imputed data).

Line plots will be generated to present the percentages of responders over time by maintenance treatment group over time (from Week 16 to Week 52) based on MCMC imputed data.

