9.1.2 Analysis

CZP plasma concentration data will be tabulated and summarized by treatment group for each visit at which samples were taken using the geometric mean, geometric coefficient of variation, geometric mean, 95% confidence interval (CI), median, minimum, maximum. For each treatment group, geometric mean plasma concentration time curves will be plotted and spaghetti plots of plasma concentration time curves will be also plotted. Individual plasma concentration time curves will be plotted with ADA titers and PASI scores. The analysis will be based on the PK-PPS and CPKS.

Initial Period

Summaries based on PK-PPS will be presented for the following treatment groups:

- CZP 200mg Q2W
- CZP 400mg Q2W

The summaries for PK-PPS will be presented for all subjects and subjects with psoriatic arthritis.

Summaries based on CPKS will be presented for the following treatment groups:

- CZP 200mg Q2W

- CZP 400mg Q2W

The summaries for CPKS will be presented for subjects with generalized pustular or erythrodermic PSO.

Combined Initial and Maintenance Period

Summaries based on PK-PPS will be presented for the following treatment groups assigned at Week 0 or Week 16:

- CZP 200mg Q2W/CZP 200mg Q2W
- CZP 400mg Q2W/CZP 400mg Q2W
- CZP 200mg Q2W/CZP 400mg Q4W

Subjects who discontinued in Initial Period will be summarized in the treatment group assigned at Week 0 (e.g. discontinued CZP 200mg Q2W in CZP 200mg Q2W/CZP 200mg Q2W and discontinued CZP 400mg Q2W in CZP 400mg Q2W/CZP 400mg Q2W). Subjects who were randomized to CZP 200mg Q2W in Initial Period, but not re-randomized at Week 16, because of escape, are summarized in the treatment group CZP 200mg Q2W/CZP 200mg Q2W. Subjects who escape during the Maintenance Period will be summarized based upon the treatment group assigned at Week 0 or Week 16 (data at the escape visit and SFU data inclusive, regardless of increase in dose).

The summaries for PK-PPS will be presented for all subjects and subjects with psoriatic arthritis.

The summaries for PK-PPS will be presented by escape during the Maintenance Period for all subjects and subjects with psoriatic arthritis.

- Non-escapers from CZP 200mg Q2W/CZP 200mg Q2W
- CZP 200mg Q2W/Esc CZP
- Non-escapers from CZP 400mg Q2W/CZP 400mg Q2W
- CZP 400mg Q2W/Esc CZP
- Non-escapers from CZP 200mg Q2W/CZP 400mg Q4W
- CZP 400mg Q4W/Esc CZP

Summaries based on CPKS will be presented for the following treatment groups:

- Subjects who only receive CZP 200mg Q2W

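### The final imputed maintenance tables count Week 16 escapers from CZP 200mg Q2W, who were never re-randomised, in the 200/200 column and not in the 200/400mg Q4W column, which depresses the displayed 200mg Q2W response

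*SAP*

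**What the plan says.** **Who is re-randomised.** SAP 2.3.1.3 applies this rule to Week 16 PASI50 responders: "Subjects initially randomized to CZP 200mg Q2W will be re-randomized (1:1) to receive either CZP 200mg Q2W or CZP 400mg Q4W". Non-responders go to open-label escape treatment. SAP 9.1.2 describes such subjects from the 200mg arm as "but not re-randomized at Week 16, because of escape".

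**How columns are defined.** SAP 3.6.1 states the general rule for subjects in the blinded part: "efficacy data will be summarized based upon the treatment group assigned at Week 0 and the treatment group assigned at Week 16". It then makes an explicit exception for Week 16 escapers and puts "escapers at Week 16 from CZP 200mg Q2W in CZP 200mg Q2W/CZP 200mg Q2W". It also lists a combined 200mg column.

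**Who is in the final tables.** SAP 3.5.9: "Escapers at Week 16 will be included in tables by blinded maintenance treatment with their observed value at Week 16", with imputed data afterwards. The same section says that the interim analysis did not do this.

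**How escapers are carried.** SAP 4.2 treats them as non-responders from escape onwards for binary variables and carries the escape value forward for continuous ones. For PASI response, step 1 of the final procedure in SAP 8.3.1 is "Identify subjects who met the escape criterion at any timepoint". Step 3 says "all visits after the point of escape will be imputed via NRI". Step 4 uses a simple proportion x/N, "where x is the number of responder and N the number of subjects in this treatment group". SAP 8.3.2 applies the same method to PGA.

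**The concern.** CZP 200mg Q2W and CZP 400mg Q4W are the only two regimens allocated by re-randomisation at Week 16, so their columns are the natural pair to read side by side. Durability of response under maintenance treatment is a secondary objective (SAP 2.1.2).

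Under the rule above, one column mixes Week 16 responders with known Week 16 failures, and the other contains responders only. The 200/200 column then describes neither the whole 200mg arm nor the subjects re-randomised to stay on 200mg Q2W. A reader of the table or line plot could conclude that 400mg Q4W maintains response better when the difference comes only from where the escapers were put.

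**Working it through.** **Inputs.** The plan gives no figure for this display, so there is none to reproduce. From Protocol 14.8.1, n = 50 on CZP 200mg Q2W. The Week 16 escape rate e (PASI50 non-response) and the later response rate s among re-randomised subjects are not in the documents; both are assumed. Only upper bounds on e can be drawn, because every PASI75 responder is also a PASI50 responder:
- 30%, from the planned 70% PASI75 rate (Protocol 14.8.1);
- 25.4%, from 74.6% PASI75 at Week 12 in C87040 (Protocol Table 5-2), a study with a single loading dose.

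**Formula.** With E = 50e escapers, each re-randomised arm has r = 50(1 - e)/2 subjects. Let the true response be s in both.
- 200/200 shows r x s/(r + E) = s(1 - e)/(1 + e).
- 200/400mg Q4W shows s.
- False gap = s x 2e/(1 + e).

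The factor 2e/(1 + e) is also the share of the 200/200 column that was never re-randomised.

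| e | share never re-randomised | gap, s = 85% | gap, s = 50% | gap, s = 30% |
|---|---|---|---|---|
| 4% | 7.7% | 6.5 points | 3.8 | 2.3 |
| 10% | 18.2% | 15.5 | 9.1 | 5.5 |
| 20% | 33.3% | 28.3 | 16.7 | 10.0 |

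**A check that needs no s.** Take Week 16 PASI50, assessed before any maintenance dose. With 5 escapers of 50, the other 45 split 22 and 23. If 22 fall in 200/200, that column shows 22/27 = 81%; the 200/400mg Q4W column shows 100% by construction. With 2 or 10 escapers, 200/200 shows 24/26 = 92% or 20/30 = 67%. A difference present before maintenance treatment starts cannot be a maintenance effect.

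**LOCF PASI score.** Escapers carry an improvement below 50%. If re-randomised subjects average 85% (assumed), the gap in mean percent improvement is at least (85 - 50) x 2e/(1 + e) = 2.7, 6.4 or 11.7 points for e = 4%, 10% or 20%.

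**Against chance.** With 20 to 24 per re-randomised arm, the SD of the difference, the square root of s(1 - s)(1/n1 + 1/n2), runs from about 10 points (s = 85%, 24 per arm) to 16 (s = 50%, 20 per arm). In simulation with identical regimens, s = 85%, and the number of escapers varying at random around e = 10%, 400mg Q4W appeared at least 10 points better in 68% of trials under the SAP rule. With both columns restricted to re-randomised subjects this fell to 15%. At e = 4% the figures were 38% and 15%.

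**The case against.** **Descriptive only.** SAP 8 limits data after Week 16 to descriptive statistics, and the final analysis plans no contrast of the two regimens. This stands and caps the severity.

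**Unaffected views exist.** This stands in large part. A reader might infer that every maintenance display is distorted; the documents do not support that.
- PASI and PGA responses have tables restricted to Week 16 responders (PASI75, PASI90, PGA) and Week 0 to 52 tables with separate re-randomised and Esc rows (SAP 8.3.1, 8.3.2).
- PASI score, DLQI, Itch, ACR and mNAPSI have observed-case tables (SAP 8.3.3, 8.3.7 to 8.3.9, 8.3.16), which Week 16 escapers leave after that visit. These also lose later escapers, so they are not a full substitute.
- The interim tables to Week 24 exclude escapers (SAP 3.5.9, 4.3, Table 8-4).

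**Direction.** A reader might infer that every variable is pushed against 200mg Q2W. That is assured for PASI and PGA response rates under non-responder imputation, and for LOCF PASI score if re-randomised subjects average above 50% improvement. For DLQI, Itch, ACR and mNAPSI it is likely but not assured. Escape depends on PASI50 alone, so an escaper's carried-forward quality-of-life, itch, joint or nail score need not be worse than the re-randomised mean. The PsA and nail subsets may contain no such escaper; any who is present does count as a non-responder in an NRI rate.

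**Size in subsets.** The figures use n = 50. The sizes of the PsA and nail sets are not given, so the figures do not carry over.

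**Not a contradiction.** SAP 3.6 allows escapers to be analysed by the last dose before escape, SAP 3.6.1 states the exception openly, and SAP 3.5.9 discloses the change from the interim. The problem is the choice. The 8.3.1 and 8.3.2 headings, which mention only escape after Week 16, might suggest that Week 16 escapers are left out. SAP 3.5.9, 3.6.1 and step 1 of the 8.3.1 procedure show that they are in.

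**Other columns also contain escapers.** PBO/PBO and 400/400 do, but those arms are not split at Week 16. For the 200mg arm the equivalent is the pooled column.

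**Conclusion.** The point holds for the final imputed (NRI, MCMC plus NRI, LOCF) tables and line plots by blinded maintenance group. For PASI and PGA rates the distortion against 200/200 is certain in direction once one 200mg subject escapes at Week 16 and s is above zero. Its size is s x 2e/(1 + e), between 3.8 and 28.3 points over s = 50% to 85% and e = 4% to 20%, all assumed values. At e = 4% it is below chance variation, but averaging would not remove it.

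What remains without an unaffected imputed counterpart is the Week 28 to 52 displays of PASI score, DLQI, Itch, ACR and mNAPSI, and the line plots in SAP 8.3.1, 8.3.2 and 8.3.9. For the PsA and nail subsets no size can be given.

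A reader might go further and infer that the evidence for efficacy, or a planned dose comparison, is compromised. It is not: no primary, secondary or interim result changes. Severity is minor to should-fix, and the low cost of correction argues for making it.

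**What to change.** In SAP 3.5.9 and 3.6.1:

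1. Restrict the split 200/200 and 200/400mg Q4W columns to subjects re-randomised at Week 16, the row definition already used in the combined-period table of SAP 8.3.1. Keep later escapers in their re-randomised arm, as non-responders or by LOCF. The false gap then falls to zero in expectation.
2. Show Week 16 escapers from CZP 200mg Q2W in the pooled 200mg column. Relabel it, for example, All CZP 200mg Q2W at Week 0, including Week 16 escapers. Footnote their number, because its N will exceed the sum of the two split columns.
3. Carry the pooled column into the line plots.
4. Footnote that 400/400 and PBO/PBO include Week 16 escapers and are comparable only with the pooled column.
5. Editorial: bring the headings on escape after Week 16, and the references to the FAS, in 8.3.1 to 8.3.3 into line with 3.5.9 and 3.6.1.

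**Cost.** SAP wording, footnotes and table programming; no new data or patients. The split columns can no longer be read directly against 400/400 or PBO/PBO. With s = 85% and e = 10% in both CZP arms, 400/400 would show 85% x 0.90 = 76.5% beside 85% in each split column. The pooled 200mg column, also 76.5%, is the like-for-like comparison, so the footnote is needed.
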